2 SYNOPSIS

Title of Study: A Phase 2/3, Randomized, Open-Label, Multi-center Study to Determine the Safety and Efficacy of Solithromycin in Adolescents (12 to 17 years of age, inclusive) and Children (≥ 2 months to < 12 years of age) with Suspected or Confirmed Community-Acquired Bacterial Pneumonia

Study No: CE01-203

Planned Number of Investigational Sites: Approximately 90

Clinical Phase: 2/3, to be conducted in the U.S. and approximately 7 additional countries in other regions of the world

Planned Study Period: Approximately 24 months (first subject visit to last subject last visit)

Objectives:

Primary

- Evaluate the safety and tolerability of solithromycin in adolescents and children with community-acquired bacterial pneumonia (CABP)

Secondary

- Evaluate the efficacy of solithromycin in adolescents and children with CABP
- Evaluate the population pharmacokinetics (PK) of solithromycin in adolescents and children with CABP

Rationale

There is a growing body of efficacy and safety data on solithromycin in adults, it was shown to be non-inferior to moxifloxacin in an adult Phase 3 trial in CABP. However, the safety and efficacy of solithromycin have not yet been studied in pediatric subjects with CABP. There is evidence of similarities in children and adults in 1) CABP definitions and pathophysiology, 2) causative organisms, 3) response to intervention, and 4) exposure-response relationship. Therefore, extrapolation of efficacy in pediatric subjects from adult clinical trial efficacy data is reasonable. A safety study in pediatric subjects with CABP, however, is needed to compare the safety and tolerability of solithromycin to comparators. This study will gather necessary safety data and, as a secondary objective, assess the efficacy of solithromycin as a CABP treatment in pediatric subjects.

Methodology

This is a phase 2/3, randomized, open-label, active control, multi-center study to assess the safety and efficacy of solithromycin in children and adolescents with CABP. After informed consent/assent is obtained, subjects will be randomized to receive solithromycin or a comparator drug, administered intravenously (IV) or by mouth (PO) in capsules or suspension formulation. Pharmacokinetic samples will be collected to assess solithromycin disposition in subjects with CABP.

Subject Participation

The duration of participation, from the signing of the informed consent form and assent (if applicable), will be up to 32 days:

- Up to 10 days of therapy (5 to 7 days with solithromycin, 5 to 10 days with comparator antibiotics)
- Up to 32 days of adverse event (AE) and serious AE (SAE) monitoring (28 \pm 4 days will be reported)

Number of Subjects Planned

400 subjects ≥ 2 months to 17 years of age, inclusive, with CABP. Subjects will be randomized (3:1) into 2 groups: solithromycin (N~300) or comparator (N~100). Randomization will be stratified by the following age groups:

Age Group 1: Adolescents from 12 years to 17 years, inclusive

Age Group 2: Children from 6 years to < 12 years

Age Group 3: Children from 24 months to < 6 years

Age Group 4: Infants from ≥ 2 months to < 24 months

A minimum of 40 subjects will be included in each age group. Approximately 20% of subjects will be enrolled in the U.S.

Diagnosis and Main Criteria for Inclusion**Inclusion Criteria:**

1. Written informed consent from parents or other legally acceptable representatives and informed assent from subject (if age appropriate according to local requirements)
2. ≥ 2 months to 17 years of age, inclusive
3. Requiring hospitalization, emergency room, or urgent care visit
4. Presence of CABP based on the following criteria within 72 hours prior to randomization:
 - History of and/or documented fever (rectal, temporal, ear, or oral temperature $\geq 38^{\circ}\text{C}$ or axillary temperature $\geq 37.5^{\circ}\text{C}$) or hypothermia (rectal, temporal, ear, or oral temperature $< 35^{\circ}\text{C}$ or axillary temperature $< 34.5^{\circ}\text{C}$)
 - AND**
 - Chest radiograph infiltrates consistent with bacterial pneumonia (or pneumonia caused by atypical bacterial agents); if a subject is outpatient and starting on oral therapy, a radiograph is not required.
 - AND**
 - Presence of **at least 2** of the following signs or symptoms:
 - a. Cough
 - b. Difficulty breathing
 - c. Production of purulent sputum
 - d. Chest pain
 - e. Grunting
 - f. Hypotension
 - g. Tachycardia, defined as follows:
 - 2 months to < 24 months: ≥ 160 beats/min
 - 24 months to < 10 years: ≥ 140 beats/min
 - ≥ 10 years: ≥ 100 beats/min
 - h. Tachypnea, defined as follows:
 - 2 months to < 12 months: ≥ 50 breaths/min
 - 12 months to < 5 years: ≥ 40 breaths/min
 - ≥ 5 years: ≥ 20 breaths/min
 - i. Physical exam consistent with pulmonary consolidation
 - AND**
 - Presence of **at least 1** of the following:
 - a. Leukocytosis ($\geq 12,000$ white blood cells [WBC]/ mm^3)
 - b. Leukopenia (< 5000 WBC/ mm^3)
 - c. $\geq 10\%$ immature neutrophils (bands) regardless of total peripheral WBC
 - d. Elevated inflammatory markers (C-reactive protein or procalcitonin)
 - e. Oxygen saturation $< 97\%$ on room air
 - f. Organism consistent with a typical respiratory pathogen identified from a blood culture or isolated from an appropriate respiratory culture/polymerase chain reaction (sputum in children old enough to produce an acceptable specimen; sample from the lower respiratory tract airways, if performed [e.g., bronchoalveolar lavage]; or pleural fluid culture)

Exclusion Criteria:

1. Confirmed or suspected respiratory tract infection attributable to sources other than community-acquired bacterial pathogens (e.g., ventilator-associated pneumonia; hospital-acquired pneumonia).
2. Received > 48 hours of potentially effective systemic antibacterial therapy for CABP immediately prior to randomization (exception: clinical or microbiological treatment failure or progression of signs or symptoms of CABP as determined by the investigator).
3. Confirmed or suspected bacterial meningitis.
4. Known active pulmonary tuberculosis.
5. Non-infectious causes of pulmonary infiltrates (e.g., cystic fibrosis, chemical pneumonitis from aspiration, hypersensitivity pneumonia).

6. Evidence or history of clinically significant medical condition that may, in the assessment of the investigator, impair study participation or pose a significant safety risk or diminish the subject's ability to undergo all study procedures and assessments.
7. Hepatic dysfunction evidenced by alanine aminotransferase (ALT) or aspartate aminotransferase (AST) >3 times upper limit of normal (ULN) or direct bilirubin greater than 2 times ULN (If direct bilirubin values are not available in a timeframe consistent with enrollment requirements, total bilirubin must be <2 times ULN).
8. Treatment with the following drugs within 72 hours prior to first dose of study drug or expected to receive these drugs during the treatment phase: drugs that potently inhibit CYP3A4 (nefazodone, fluconazole, ketoconazole, conivaptan, diltiazem, verapamil, aprepitant, imatinib, protease inhibitors, clarithromycin, ciprofloxacin, erythromycin, itraconazole, mibefradil, posaconazole, telithromycin, and voriconazole); CYP3A4 inducers (rifampin, rifabutin, phenytoin, fosphenytoin, carbamazepine, phenobarbital, rufinamide, modafinil, armodafinil, etravirine, efavirenz, nevirapine, rilpivirine, bosentan, troglitazone, pioglitazone, and St. John's wort). In addition, the following drugs may not be co-administered with solithromycin in this trial due to the potential for adverse drug-drug interaction: digoxin, colchicine, midazolam, quinidine, ergotamine, dihydroergotamine, rivaroxaban, apixaban, dabigatran, edoxaban, cisapride, cyclosporine, sildenafil, astemizole, and alfentanil.
9. Breast-feeding females.
10. Positive pregnancy test in females of childbearing potential.
11. History of anaphylaxis to macrolide antibiotics.
12. Previous participation in this study.
13. Subject has received any investigational drug studied under an Investigational New Drug application in the U.S. or under a Clinical Trial Application in the relevant country outside of the U.S. where the subject is being enrolled, taken within 4 weeks before administration of the first dose of study drug.
14. End Stage Renal Disease (dialysis requiring) OR severe renal impairment (defined as serum creatinine > 1.5 fold ULN for age).

Test Product

Dose and Mode of Administration: Solithromycin will be administered IV or PO according to the tables below. If dosing begins with oral therapy, the Day 1 dose will be a loading dose. No loading doses are used with IV solithromycin administration or if switched to oral administration. An IV-to-PO switch can occur after the first IV dose. Subjects starting with oral therapy will receive 5 days of solithromycin treatment and those starting with IV therapy (regardless of if and when they switch to oral therapy) will receive 7 days of solithromycin treatment.

Capsule Dosing Regimens

Age (years)	Weight	Route	Formulation	Day 1 (Max dose: 800 mg)	Days 2 to 5 (Max dose: 400 mg)
6 to 17	>30 kg	PO	Capsules	800 mg	400 mg
	>20 to 30 kg	PO	Capsules	600 mg	400 mg
	≤20 kg	PO	Capsules	400 mg	200 mg

Suspension Dosing Regimens

Age (years)	Route	Formulation	Day 1 (Max dose: 800 mg)	Days 2 to 5 (Max dose: 400 mg)
12 to 17	PO	Suspension	20 mg/kg (800 mg)	10 mg/kg (400 mg)
6 to <12	PO	Suspension	20 mg/kg	10 mg/kg
2 to <6	PO	Suspension	20 mg/kg	10 mg/kg
2 mo to <2	PO	Suspension	20 mg/kg	10 mg/kg

Intravenous Dosing Regimens

Age (years)	Route	Formulation	Days 1 to 7 (Maximum dose: 400 mg)
12 to 17	IV	Solution	8 mg/kg
6 to <12	IV	Solution	8 mg/kg
2 to <6	IV	Solution	8 mg/kg
2 mo to <2	IV	Solution	8 mg/kg

Intravenous to Oral Dosing Regimens

Age (years)	Route	Oral Formulation	Day 1 to Last IV Dosing Day (Max dose: 400 mg)	First Oral Dosing Day to Day 7 (Max dose: 400 mg) ^a
12 to 17	IV/PO	Suspension or Capsules	8 mg/kg	10 mg/kg (400 mg)
6 to <12	IV/PO	Suspension or Capsules	8 mg/kg	10 mg/kg
2 to <6	IV/PO	Suspension	8 mg/kg	10 mg/kg
2 mo to <2	IV/PO	Suspension	8 mg/kg	10 mg/kg

a. The adult dose should be administered unless the subject weighs <40 kg, in which case they receive 10 mg/kg on the first oral dosing day through Day 7. The capsule dose is rounded upwards to the nearest 200 mg.

Comparator Therapy

Dose and Mode of Administration: Comparators will be selected according to subject age and are consistent with current recommendations for treatment of CABP in children. A dosing table is provided below.

Children \geq 2 months to <5 years of age:

- a. Ceftriaxone IV **OR**
- b. Ampicillin IV **or** amoxicillin IV **OR**
- c. Amoxicillin-clavulanic acid PO **or** IV **or** amoxicillin PO

Children 5 to 17 years of age (inclusive):

- a. Ceftriaxone IV **OR**
- b. Ampicillin IV **or** amoxicillin IV **OR**
- c. Amoxicillin-clavulanic acid PO **or** IV **or** amoxicillin PO

Azithromycin IV/PO or erythromycin lactobionate IV or erythromycin PO may be added to any of the treatment regimens above. Azithromycin is also acceptable as a first line of treatment.

	United States	Rest of the World
Amoxicillin	45-90 mg/kg/day orally in 2 or 3 divided doses; not to exceed 3 g/day	45-90 mg/kg/day orally in 2 or 3 divided doses; not to exceed 3 g/day 50-100 mg/kg/day intravenously in equally divided doses every 6 hours
Amoxicillin-clavulanic acid	Children <40 kg: amoxicillin component 90 mg/kg/day orally in divided doses given every 12 hours [4000 mg/day max dose] Children ≥40 kg, 875 mg orally every 12 hours or 500 mg orally every 8 hours [4000 mg/day max dose]	Children <40 kg: 20 mg/5 mg/kg/day to 60 mg/15 mg/kg/day given orally every 8 hours Children ≥ 40 kg: One 500 mg/125 mg dose given orally every 8 hours
Amoxicillin-clavulanic acid	-	Children >4kg but< 40kg: amoxicillin component 25 mg/kg intravenously every 8 hours [1000 mg max dose] Children ≥ 40 kg: amoxicillin component 1000 mg intravenously every 8 hours
Ampicillin	150-200 mg/kg/day intravenously in equally divided doses every 6 hours	-
Azithromycin	10 mg/kg intravenously/orally on day 1 [500 mg maximum dose] followed by 5 mg/kg orally every 24 hours [250 mg maximum dose]	10 mg/kg orally on day 1 [500 mg maximum dose] followed by 5 mg/kg orally every 24 hours [250 mg maximum dose]
Ceftriaxone	50-75 mg/kg/day intravenously in equally divided doses every 12 hours; total daily dose should not exceed 2 g	50-80 mg/kg intravenously once daily
Erythromycin	40 mg/kg/day orally every 6 hours	30-50 mg/kg/day orally every 6 hours
Erythromycin lactobionate	15 to 20 mg/kg/day intravenously in equally divided doses every 6 hours	50 mg/kg/day intravenously/orally in equally divided doses every 6 hours

Note: if doses of comparator drugs noted in the dosing table above differ from those prescribed per standard of care, a site can use the locally prescribed dose.

Intravenous-to-oral switch:

Subjects receiving an IV comparator drug in any age group may be switched to oral treatment using amoxicillin-clavulanic acid PO (amoxicillin component 45 mg/kg every 12 hours; subjects weighing ≥ 40 kg, 875 mg every 12 hours or 500 mg every 8 hours) or amoxicillin alone (45 mg/kg every 12 hours, up to a maximum of 4 g/day).

Duration of Treatment: 5 to 10 days. The exact duration of treatment may be determined at the investigator's discretion.

Addition of expanded gram-positive coverage to treatment and comparator groups will be allowed if empiric therapy for methicillin-resistant *Staphylococcus aureus* is desired per local standard of care.

Criteria for Evaluation:

Safety:

Any study team member may perform safety assessments. An independent Data Monitoring Committee will assess the overall study status and safety of subjects at intervals outlined in the committee's charter and will make recommendations to the sponsor on continuing or modifying the study based on these assessments.

Efficacy:

A health care provider designated as a subinvestigator blinded to treatment allocation at the site will document clinical response at specified time points during the study.

Pharmacokinetics:

The table below provides the optimal plasma sampling collection windows for solithromycin according to route of administration. Every effort should be made to collect at least 2 PK samples on Day 1 and at least 2 PK samples on days 3 through 7 during these windows (not to exceed 6 samples total); however, samples obtained outside of the sampling windows are acceptable. Lack of collection of samples or collection outside the optimal windows will not be considered protocol deviations.

IV Time after dose	Oral Time after dose
Prior to dosing (within 1 hour) ^a	Prior to dosing (within 1 hour) ^a
End of infusion (within 10 minutes)	0.5–1.5 hours
2–4 hours	2–4 hours
8–10 hours	8–10 hours
16–18 hours	16–18 hours
20–<24 hours	20–<24 hours

^a Not applicable to Day 1 samples.

Statistical Methods and Data Analysis

Efficacy population: All subjects who are randomized.

Safety population: All subjects who receive at least 1 dose of study drug.

PK population: All subjects who receive at least 1 dose of solithromycin and have at least 1 evaluable PK sample.

MicroITT population: Randomized subjects who have a microbiologically confirmed baseline pathogen.

Safety:

New events that occur or pre-existing conditions that worsen in frequency or intensity will be reported as AEs or SAEs. AEs will be reported for 16 days and SAEs for 28 days post-randomization. The investigator will provide date of onset and resolution, intensity, frequency, actions taken, changes in study drug dosing, relationship to study drug, and outcome. Laboratory determinations performed by local laboratories including hematology values (hemoglobin, hematocrit, WBC count with differential, and platelet count) and serum chemistry values (blood urea nitrogen, calcium, serum creatinine, potassium, sodium, AST, ALT, alkaline phosphatase, total and direct bilirubin, and albumin) obtained within 72 hours prior to the first dose of study drug and while the subject is on therapy will be recorded. Baseline and on-study microbiological cultures of blood, cerebrospinal fluid (CSF), pleural fluid, and respiratory secretions will be recorded if obtained within 72 hours prior to the first dose of study drug and while the subject is on therapy. If an AE or SAE occurs, concomitant medications will be recorded at the time of the event.

Primary safety endpoints will be the proportion of subjects experiencing an AE and the proportion of subjects discontinuing study drug due to a related AE. Additional safety analyses include summaries of AEs, descriptive statistics of laboratory values, frequency distributions and shift tables summarizing abnormal laboratory values, descriptive statistics of vital signs, and frequency distributions of abnormal physical examinations.

Efficacy:

The primary efficacy endpoint is defined as clinical improvement on the last day of treatment (end of treatment response), and the secondary efficacy endpoints are defined as early clinical response at Days 2-4 and clinical success (i.e., cure) at the short-term follow-up visit (16 days [+/- 4 days] post-randomization).

Pharmacokinetics:

Population PK methodologies using nonlinear mixed effects modeling in NONMEM will be used to analyze the concentration data. Data will be reviewed during the study to evaluate PK of solithromycin in pediatric CABP patients. The influence of covariates on PK parameters will be explored. Monte Carlo simulations will be used to evaluate optimal drug exposure. The relationship between drug exposure and safety events will be evaluated by calculating the proportion of subjects with AEs and SAEs at different exposure levels.

Table 1 Schedule of Assessments and Procedures

Activity	Screening/Baseline (Day -3 through Day -1) ^a	Treatment Period		Follow-Up	
		Treatment Days up to Last Day of Treatment ^b	Last Day of Treatment (+48 hours)	Day 16 Post Randomization ^{c, d} (±4 days)	Day 28 Post Randomization ^d (±4 days)
Informed consent form	X				
Demographic data	X				
Eligibility criteria	X				
Randomization	X				
Medical history	X				
Physical examination	X	X ^c	X	X	
Vital signs ^e	X	X ^c	X	X	
Chest x-ray ^f	X				
Study-required safety labs ^g	X ^h	X ⁱ	X ^j	X ⁱ	X ⁱ
Review of standard-of-care data: Safety labs ^{g, k} Microbiology assessments ^l Radiological imaging ^m Non-pharmacological treatments ⁿ	X	X	X	X	
Pregnancy test ^o	X	X ^p			
Concomitant medications ^q	X	X	X		
Study drug or comparator administration ^r		X	X		
Pharmacokinetic sampling ^s		X	X		
Adverse event assessment	X	X	X	X	
Serious adverse event assessment	X	X	X	X	X

Activity	Screening/Baseline (Day -3 through Day -1) ^a	Treatment Period		Follow-Up	
		Treatment Days up to Last Day of Treatment ^b	Last Day of Treatment (+48 hours)	Day 16 Post Randomization ^{c, d} (±4 days)	Day 28 Post Randomization ^d (±4 days)
Clinical outcomes and symptom assessments: Early Clinical Response, End of Treatment, and Follow-Up Post Treatment ^t	X	X ^u	X ^v	X ^w	

- a Screening/baseline can occur up to 72 hours prior to randomization. Standard-of-care laboratory data and radiological imaging from up to 72 hours prior to randomization may be used as screening procedures. Screening/baseline and first day of treatment may be the same day.
- b Treatment period is 5 to 7 days for solithromycin and 5 to 10 days for comparators. These assessments and procedures may be done prior to Day 3 if the subject is discharged from the hospital before Day 3.
- c Record vital signs for each day available. Physical examinations should be recorded from baseline and the Day 3 to 4 visit (early clinical outcome assessment) and at the Last Day of Treatment visit.
- d Every effort should be made to bring the subject back. If the subject is unable or unwilling to return, the AEs/SAEs must be collected via telephone/other media.
- e Vital signs taken at the closest time post-drug administration should be noted. If vital signs following drug administration are not available, record the first value of the day.
- f Screening chest x-ray does not need to be repeated if a standard-of-care chest x-ray was performed within 72 hours of randomization. Subjects that are outpatient and starting on oral therapy do not need a screening x-ray.
- g Local laboratory; includes hemoglobin*, hematocrit*, white blood cell count with differential*, platelet count*, blood urea nitrogen*, calcium*, serum creatinine, potassium*, sodium*, aspartate aminotransferase, alanine aminotransferase, alkaline phosphatase*, total and direct bilirubin, and albumin*. If laboratories with * designation are not obtained, it will not result in a protocol deviation.
- h A separate study sample is not required if safety labs above are obtained at baseline per standard of care. If multiple laboratory tests are obtained within 72 hours of randomization, record test results closest to randomization.
- i Every effort should be made to obtain safety labs 72 (±24) hours after the first dose to include aspartate aminotransferase, alanine aminotransferase, alkaline phosphatase, total and direct bilirubin, and white blood cell count with differential. A separate study sample is not required if safety labs above are obtained within the visit window per standard of care.
- j Safety labs must be collected on the last day of dosing or within 48 hours after the last dose. A separate study sample is not required if safety labs above are obtained on the last day of dosing or within 48 hours after the last dose per standard of care.
- k Record the safety labs if performed per standard of care; if multiple laboratory tests are obtained on the same day, record test results closest to administration of study drug.
- l Microbiological assessments will be recorded if performed per routine medical care. These include cultures from sterile body fluids and molecular and serologic tests for *Mycoplasma pneumoniae* and *Chlamydia pneumoniae*.
- m Radiological imaging of the chest, including chest x-ray or computed tomography (CT) scan, will be recorded if performed per routine medical care.
- n Non-pharmacologic treatments (such as operative procedures) will be recorded if performed per routine medical care.
- o Female subjects of childbearing potential within 24 hours of first dose.
- p If the screening visit for females occurred greater than 24 hours before receiving the study drug.

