8.1 Inclusion Criteria

1. Written informed consent from parent or other legally acceptable representative and informed assent from subject (if age appropriate according to local requirements)
2. ≥ 2 months to 17 years of age, inclusive
3. Requiring hospitalization, emergency room, or urgent care visit
4. Presence of CABP based on the following criteria within 72 hours of randomization:
 - History of and/or documented fever (rectal, temporal, ear, or oral temperature $\geq 38^{\circ}\text{C}$ or axillary temperature $\geq 37.5^{\circ}\text{C}$) or hypothermia (rectal, temporal, ear, or oral temperature $< 35^{\circ}\text{C}$ or axillary temperature $< 34.5^{\circ}\text{C}$)

AND

- Chest radiograph infiltrates consistent with bacterial pneumonia (or pneumonia caused by atypical bacterial agents); if a subject is outpatient and starting on oral therapy, a radiograph is not required.

AND

- Presence of **at least 2** of the following signs or symptoms:
 - a. Cough
 - b. Difficulty breathing
 - c. Production of purulent sputum
 - d. Chest pain
 - e. Grunting
 - f. Hypotension
 - g. Tachycardia defined as follows:
 - 2 months to < 24 months: ≥ 160 bpm
 - 24 months to < 10 years: ≥ 140 bpm
 - ≥ 10 years: ≥ 100 bpm
 - h. Tachypnea, defined as:
 - 2 months to < 12 months: ≥ 50 breaths/minute
 - 12 months to < 5 years: ≥ 40 breaths/minute

- ≥ 5 years: ≥ 20 breaths/minute
 - i. Physical exam consistent with pulmonary consolidation
- AND**
- Presence of **at least 1** of the following:
 - a. Leukocytosis ($\geq 12,000$ white blood cells [WBC]/ mm^3)
 - b. Leukopenia ($< 5,000$ WBC/ mm^3)
 - c. $\geq 10\%$ immature neutrophils (bands) regardless of total peripheral WBC
 - d. Elevated inflammatory markers (C-reactive protein or procalcitonin)
 - e. Oxygen saturation $< 97\%$ on room air
 - f. Organism consistent with a typical respiratory pathogen identified from a blood culture or isolated from an appropriate respiratory culture/polymerase chain reaction (sputum in children old enough to produce an acceptable specimen; sample from the lower respiratory tract airways, if performed [e.g., bronchoalveolar lavage]; or pleural fluid culture)

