10.6 Clinical Efficacy Outcomes Assessments Time Points

Clinical outcomes assessments will be performed by a blinded investigator at the study site. At each time point, the site blinded investigator will evaluate signs and symptoms and record physical findings of CABP. These assessments will include cough, difficulty breathing, purulent sputum production, chest pain, grunting, hypotension, tachycardia, tachypnea, and evidence of pulmonary consolidation (further details are in the Blinded Investigator Plan). If symptoms and physical exam findings are available in the medical record per standard of care, these can be used for the clinical outcomes assessments.

Clinical efficacy outcomes assessments will be performed at the following time points:

- A baseline assessment of signs, symptoms, and physical exam findings will be completed at screening
- Clinical improvement on the last day of treatment (+48 hours) (primary efficacy endpoint)
- Clinical improvement on Day 3 or 4. If the subject is discharged from the hospital prior to Day 3, assessment may be recorded on Day 2. A return visit is not required to perform this assessment if the subject has been discharged prior to the assessment.
- Clinical cure during SFU at 16 days (+/-4 days) post-randomization (secondary efficacy endpoint). This assessment will be conducted if information is available per standard of care and may be recorded from the medical record via phone/other media.

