10.8 Clinical Cure Definition (Day 16 Post Randomization [±4 Days])

Clinical cure is defined as resolution of all presenting signs and symptoms of CABP (excluding cough), no development of new sign or symptoms of CABP, and no requirement for alternative antimicrobial therapy.

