10.4 Secondary Efficacy/Clinical Outcomes

Evaluation of clinical signs and symptoms of CABP, requirement for additional or alternative antimicrobial therapy, and efficacy will be performed by a blinded investigator or designee at the site. Outcomes will be assessed at the following time points:

- Baseline clinical signs and symptoms assessment
- Clinical improvement on Day 3 - 4. If the subject is discharged from the hospital prior to Day 3, assessment may be recorded on Day 2.
- Clinical improvement on the last day of treatment (+48 hours)
- Clinical cure during short-term follow up at 16 days (\pm 4 days) after randomization (secondary efficacy endpoint). This assessment will be conducted if information is available per standard of care and may be recorded from the medical record via phone or other media.

Efficacy will be quantified as a binary variable at each timepoint listed above using the algorithm specified in Appendix 2. Clinical improvement is defined as improvement (compared to baseline) of at least 1 of the presenting signs and symptoms of CABP with no deterioration in any presenting sign or symptom of CABP (compared to baseline), no development of new sign or symptom of CABP, and no requirement for additional or alternative antimicrobial therapy. Clinical cure is defined as resolution of all presenting signs and symptoms of CABP (excluding cough), no development of new sign or symptoms of CABP, and no requirement for additional antimicrobial therapy. Clinical improvement and cure will be determined using the specific signs and symptoms data recorded on the eCRF, as well as a separate question on the eCRF concerning additional antimicrobial therapy. These questions will be completed by the blinded investigator (or potentially unblinded investigator in the case of screening evaluation), who will be supplied with information according to the blinded investigator plan.

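### The tachypnea limit drops from 40 to 20 breaths/min at age 5 and is also an efficacy sign, so as written a child of 5 or over recorded at 20 or more on Day 16 would not count as cured

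*Protocol*

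**What the plan says.** Inclusion criterion 4 in the Protocol Synopsis sets three tachypnea limits: "2 months to < 12 months: ≥ 50 breaths/min", "12 months to < 5 years: ≥ 40 breaths/min" and "≥ 5 years: ≥ 20 breaths/min". Section 8.1 repeats the last as "≥ 5 years: ≥ 20 breaths/minute", and Section 10.9, which lists the signs and symptoms used for efficacy, carries the same three limits. The three places agree, so this is not a slip in one of them.

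Section 10.6 gives the efficacy assessment to a blinded investigator: "These assessments will include cough, difficulty breathing, purulent sputum production, chest pain, grunting, hypotension, tachycardia, tachypnea, and evidence of pulmonary consolidation". Section 10.8 defines cure as "resolution of all presenting signs and symptoms of CABP (excluding cough), no development of new sign or symptoms of CABP", and no alternative antimicrobial therapy may be needed. Cough is the only sign exempted from having to resolve. Clinical improvement, in Section 10.7 and SAP 10.4, needs at least one presenting sign better, none worse, and "no development of new sign or symptom of CABP".

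SAP 10.4 derives both outcomes from the individual signs entered on the eCRF, by an algorithm placed in SAP Appendix 2. It reports them by arm and by consolidated age group (2 months to <6 years, 6 to 17 years), with exact 95% confidence intervals, in Table 14.5.1.

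**The concern.** As an entry criterion, a low limit for older children does little harm, because a second sign and a further laboratory, saturation or culture criterion are also required. As an efficacy sign it works the other way. Tachypnea must be absent for cure, and its appearance after baseline counts as a new sign. A child of 5 or over who has recovered but breathes at 20 or a little above would be scored as a failure, while a child slightly under 5 at the same rate would be scored as cured.

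At stake is how Table 14.5.1 is read. The 6 to 17 year group is scored entirely under the limit of 20. The younger group is scored under 50, 40 and, for its 5-year-olds, 20. A lower cure rate in the older group could be taken for an age effect on treatment when part of it comes from the scoring rule.

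**Working it through.** **1. Size of the step.** Inputs are the limits in Protocol 10.9.

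- Tachypnea: 50 to 40 is a fall of (50 − 40)/50 = 20%; 40 to 20 is (40 − 20)/40 = 50%.
- Tachycardia, for comparison: 160 to 140 is 12.5%; 140 to 100 is 28.6%.

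**2. The cure rule applied literally.** Assume every other sign has resolved and no further antibiotic is needed.

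| Age | Baseline rate | Day 16 rate | Result under 10.8 |
|---|---|---|---|
| Just under 5 | 18, 30 or 45 | 18 to 39 | Cured |
| 5 or over | 18, 30 or 45 | 18 or 19 | Cured |
| 5 or over | 30 or 45 | 20 to 39 | Not cured: presenting sign unresolved |
| 5 or over | 18 | 20 to 39 | Not cured: new sign |

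From age 5, a Day 16 rate of 20 or more fails whatever the baseline.

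**3. The improvement rule.** Suppose a child of 5 or over has another sign improved.

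- Entered at 18, later 20 or more: fails, because tachypnea is new.
- Entered at 30, later 20 to 30: passes. The sign persists but has not worsened.
- Entered at 30, later 39: fails if a higher rate is read as deterioration.

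Apart from true worsening, the effect on improvement is confined to children who entered below 20.

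**4. How many recovered children might be caught.** The documents give no resting rates, so the means and SDs below are assumptions. Rates are taken as normally distributed and recorded in whole breaths.

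P(rate ≥ 20) = 1 − Φ((19.5 − mean)/3)

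| Assumed group | Mean | z | Share at 20 or more |
|---|---|---|---|
| 5 to 11 years | 18 | 0.50 | 31% |
| 5 to 11 years | 20 | −0.17 | 57% |
| 5 to 11 years | 22 | −0.83 | 80% |
| Adolescents | 16 | 1.17 | 12% |

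For ages 1 to <5 against the limit of 40, with SD 5: 1 − Φ((39.5 − mean)/5) gives 0.1% at mean 24, 1.1% at mean 28 and 2.9% at mean 30.

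**5. Effect on the cure rate.** If a share f of truly cured children is recorded at 20 or more, scored cure = true cure × (1 − f). With an assumed true cure of 90%:

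- f = 10%: 0.90 × 0.90 = 81.0%
- f = 25%: 0.90 × 0.75 = 67.5%
- f = 50%: 0.90 × 0.50 = 45.0%

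The 6 to 17 year group mixes school-age children and adolescents, so on the assumptions in step 4 its f lies somewhere between 12% and 80%, depending on the mix and the true mean.

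**The case against.** **The scoring rule has not been seen in full.** SAP 10.4 points to Appendix 2, and Protocol 10.6 refers to the Blinded Investigator Plan for detail. Neither is in the text available. The eCRF may record tachypnea as the assessor's judgement and not from the measured rate. A Day 16 assessment taken by telephone or from records may have no rate at all. A reader might infer that a recovered school-age child cannot be scored as cured. The documents support only that, as written, such a child would not be. This stands and limits the claim.

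**The size rests on outside assumptions.** A reader might infer that Day 16 cure at ages 5 to 11 largely measures resting breathing rate. That follows only towards the upper end of the assumed range; at mean 18 the share is 31%. This also stands.

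**Clinical improvement is little affected.** End-of-treatment improvement is the protocol's primary efficacy endpoint, and only children below 20 at entry can fail it through new tachypnea. Few may enter with pneumonia at such a rate. That is fair, and the number cannot be estimated from the documents.

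**Little decision weight.** Efficacy is a secondary objective, is not powered for comparison, and is reported descriptively; pediatric efficacy is extrapolated from adults. Enrollment stopped below a quarter of 400. A reader might infer that the limit biases the arm comparison. It applies equally to both arms under age-stratified randomization, so it should lower both rates and not favor one. An equal f would dilute a true difference by the factor 1 − f (10 points becomes 7.5 at f = 25%), but no between-arm test is planned. The primary safety endpoints are untouched.

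**Changing the limit now would be worse.** New limits for efficacy would redefine a protocol endpoint after an open-label trial had ended. That is correct, and no new limit is proposed here.

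What survives is the literal reading of Protocol 10.8 with 10.9. Nothing in the available text lets the assessor set the limit aside, and nothing explains why the limit halves at age 5.

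**Conclusion.** The point holds as a statement about the written definitions. From age 5, a recorded Day 16 rate of 20 or more blocks cure through one clause or the other, while just under age 5 rates up to 39 do not. A child of 5 or over who entered below 20 and is later recorded at 20 or more also fails improvement.

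The consequence is a descriptive cure rate in older children that may read low and is not like for like with the younger consolidated group. The 31% to 80% range (12% for adolescents) depends on assumed means and SDs and on the eCRF sign following the measured rate. If the unseen algorithm or plan treats tachypnea differently, the effect could be smaller or absent. This is a matter of interpreting a secondary efficacy table; it does not threaten the trial's primary conclusions.

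**What to change.** Leave the entry criterion and the protocol-defined endpoints as they are.

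1. Add to SAP 10.4 and Table 14.5.1 a sensitivity analysis, labelled as added after termination. It recomputes the three efficacy rates (early response, end of treatment, Day 16 cure) with the tachypnea item removed from every clause, by arm and consolidated age group, and for ages 5 and over.
2. Report, in the same rows, how many subjects fail each endpoint on tachypnea alone. Removing the item can only raise the cure count. For improvement it can also lower the count, where tachypnea was the only sign that improved, so show changes in both directions.
3. The sponsor should confirm how a recorded respiratory rate maps to the tachypnea sign, including when Day 16 is done by telephone or from records, and reconcile the limit for ages 5 and over with its use in the cure definition.

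The cost is a few descriptive rows from signs already recorded at each assessment, and a post hoc label. SAP Section 2 already allows added analyses if they are descriptive. The sensitivity rate would also pass children whose raised rate is a true residual sign, so it should be read beside the protocol-defined rate and not in its place.
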